9.8.4.2 Secondary Endpoints and Associated Hypotheses

The secondary endpoints in this study are:

- Type and frequency of Adverse Events and Device Deficiencies.
 - Functional responder rates with an objective performance criteria (OPC) of 85% as measured by the KOOS questionnaire for all subjects (CR FB and PS FB combined) at the 1 year timepoint.
- The change from preoperative baseline to the 6 week, 6 month, 1 year, 2 year and 5 year timepoints in functional outcomes and quality of life assessments, as measured using additional patient reported outcomes measures (PROMS):
 - o AKS 2011
 - KOOS (all subscores)
 - FJS-12 (changes post-operatively only)
 - o *EQ-5D-5L*
- Implant survivorship of the ATTUNE Cementless FB Tibial Base using Kaplan-Meier survival analysis at 1, 2 and 5 year timepoints.
- Investigator-conducted radiographic analysis of the tibial and patellar components at 6 weeks/6 months, 1, 2 and 5 years after surgery.

All secondary endpoint analyses may be conducted after all patients have passed the recommended study window (ex. with a 2-year follow-up analysis conducted after all subjects have passed 790 days post-op). All analyses at these time points will be conducted again with final data, along with endpoints which have a 5-year follow-up time point, with locked data at the close of the study.

A Kaplan-Meier survivorship model will be used to estimate survivorship rates (where a revision is defined in Section 8.6) along with a two-sided, log-log based 95% confidence intervals; this analysis will be conducted on the Safety analysis set.

The types and frequencies of adverse events that occur throughout the study will be tabulated by MedDRA system organ class (SOC) and preferred term (PT) for all Subjects in the Safety analysis set. The proportion of Subjects experiencing each complication (PT within SOC) will be presented, and a 95% confidence interval will be estimated with the binomial exact method.

All other specified secondary endpoints will be presented with statistical summaries at each respective time point; these secondary endpoint analyses will be carried out with all data on subjects in the Per Protocol analysis set.

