7 STUDY DESIGN

This study is designed as a post-market, prospective, multi-center, non-randomized, non-comparative, single arm observational study. Level of evidence: III. The sample size for this study is anticipated to be a minimum of 600 subjects. A minimum of each of the following variants must be included:

- 300 ATTUNE Cementless Cruciate Retaining Fixed Bearings
- 300 ATTUNE Cementless Posterior Stabilizing Fixed Bearings
- Up to 300 ATTUNE Cementless Patellae (if available in United States market during the clinical study)

There will be a maximum of 25 sites in the United States. The study will allow for a minimum of 600 subjects to be implanted: 300 ATTUNE Cementless Cruciate Retaining Fixed Bearing (CR Femoral with CR or MS Tibial Insert) TKAs, 300 ATTUNE Cementless Posterior Stabilizing Fixed Bearing (PS Femoral with PS Tibial Insert) TKAs, and up to 300 ATTUNE Cementless Patellae (if market available) will be included in the DSJ_2019_05, Rev D (FINAL)

DePuy Synthes Products, Inc. - Confidential 24 August 2022

total sample. It is expected that each site will implant approximately 30 subjects (maximum of 50 per site). Treatment assignment in this study is not randomized. Sites are able to enroll subjects with the required variants, any allowed configuration until the minimum of 300 cases for that variant (CR FB or PS FB) is met. Once the cases for any particular variant are met, sites will continue to enroll the remaining variants until their site maximum of 50 subjects is met. Details regarding sample size are presented in Section 9.7.

The Sponsor will monitor overall project enrollment. The Sponsor can authorize a shift of a group of Subjects from one site to another to maintain project timelines. For example, the Sponsor can reduce the cohort of a slow-enrolling site to a faster-enrolling site and the faster-enrolling site will assume responsibility for the reallocated cohort.

Primary Endpoint analyses will be conducted after 225 patients who have undergone TKA have passed the 1 year preferred window for submission to regulatory authorities. The remaining follow-up through 5 years will further evaluate mid-term outcomes and support post-market clinical follow-up commitments.

The Investigator should follow their current standard of care with respect to patellar resurfacing. Specifically, the Investigator can choose to:

- resurface the patella with a cemented ATTUNE patella.
- leave the patella unresurfaced.

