Study subjects may be implanted with the ATTUNE Cemented Patella, ATTUNE Cementless Patella (after product availability), or not undergo patella resurfacing as part of their study procedure.

If	Then
the site is located in the US and the patella is resurfaced using an ATTUNE Cemented Patella	The site is not permitted to use DePuy Synthes Antibiotic Impregnated Bone Cement (off-label use). If this occurs, a Protocol Deviation CRF must be completed and the patient will be discontinued from the study (Study Completion/Discontinuation eCRF). The subject will be replaced with another enrolled subject.
the patella is resurfaced using an ATTUNE Cementless Patella	In this study, bone cement must not be used with the ATTUNE Cementless Patella. If bone cement is used, a Protocol Deviation CRF must be recorded and the patient will continue in the study as part of the Safety Population.

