9.8.4 Primary and Secondary Endpoints and Associated Hypotheses

Each endpoint below will be analyzed for all knees and separately for primary and revision procedures and CR FB (CR or MS Tibial Inserts) and PS FB configurations, unless otherwise specified.

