9.8.4.3 Additional Endpoints

Additional endpoints include:

- Implant survivorship of the ATTUNE Cementless FB Tibial Base using Kaplan-Meier survival analysis at 3 and 4 year timepoints.
- To evaluate the duration of surgery ("skin-to-skin" time) for all surgeries, with analysis stratified by cemented/Cementless patella usage.

Duration of surgery ("skin to skin" time) may be analyzed any time after all subjects have been enrolled and undergone surgery. All other post-operative tertiary endpoints may be conducted after all subjects have passed the preferred post-op window. All analyses at these time points will be conducted again with final data, along with endpoints which have a 5-year follow-up time point, with locked data at the close of the study.

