CE mark & 510(k) clearance	Tibial Inserts	Fixed Bearing (FB)	Posterior Stabilized (PS)	sizes 1-10 and thicknesses from 5, 6, 7, 8, 10, 12, 14, 16, 18mm. Additional thicknesses 20 & 22mm are available for the PS inserts. The distal surface has features that secure the insert to the FB tibial base. Tibial inserts are sterilized using gamma irradiation.
510(k) clearance	Tibial Inserts	Fixed Bearing (FB)	Medial Stabilized (MS)	The ATTUNE Medial Stabilized tibial inserts are asymmetrical fixed bearing tibial inserts that will form part of the ATTUNE Knee system. They are designed to work with the ATTUNE CR femur and any of the ATTUNE Fixed Bearing Tibial Base options. They are manufactured from AOX Antioxidant

DSJ_2019_05, Rev D (FINAL) 24 August 2022 DePuy Synthes Products, Inc. - Confidential

			UHMWPE and are available in right and left sizes 1-10 and thickness from 5, 6, 7, 8, 10, 12, 14 and 16. Tibial inserts are sterilized using gamma irradiation.	
CE mark & 510(k) Cemented Patellaes	Medial Offset	The patellar components are manufactured from UHMWPE and are available in two styles, medialized dome and medialized anatomic. They are available in 5 sizes with proportionally		
	Anatomic	increasing thicknesses from 8.5 to 10.5 mm. Patellar components are sterilized using gamma irradiation. They are available for cemented use only.		
		Medial Offset	The cementless patellar components are manufactured from UHMWPE overmolded onto 3D printed titanium conforming to	
510(k) clearance	Cementless Patellaes	Anatomic (if available during enrolment)	ASTM standard F-3001 and the bone opposing surfaces are comprised of 3D printed porous coating technology. The anterior surface is designed to work with currently available ATTUNE CR and PS femoral components. They are available in 4 sizes with proportionally increasing thicknesses from 9.0 to 10.5 mm. Patellar components are sterilized using gamma irradiation.	

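### The planned breakdowns in section 9.8.4 would mix cemented and cementless patellae in the patellar radiographic endpoint; that table should be split by fixation type

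*Combined protocol and SAP*

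**What the plan says.** The radiographic secondary endpoint in section 9.8.4.2 is "Investigator-conducted radiographic analysis of the tibial and patellar components at 6 weeks/6 months, 1, 2 and 5 years after surgery". It does not name the type of patella. Table 6-1 describes it as an analysis of the radiographic interface.

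The breakdowns are set once, in section 9.8.4: "Each endpoint below will be analyzed for all knees and separately for primary and revision procedures and CR FB" and PS FB configurations, unless something else is specified. For the radiographic endpoint nothing else is specified. Section 9.8.4.2 says that "All other specified secondary endpoints will be presented with statistical summaries at each respective time point", on the Per Protocol set.

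Three patellar treatments are allowed. Section 8.2.3 states: "Study subjects may be implanted with the ATTUNE Cemented Patella, ATTUNE Cementless Patella (after product availability), or not undergo patella resurfacing". Sections 7 and 9.2 leave the choice to the surgeon. Section 7 caps cementless patellae at 300, conditional on US market availability, and sets no minimum.

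Patella fixation is used as a stratum once, in section 9.8.4.3, where duration of surgery is to be evaluated "for all surgeries, with analysis stratified by cemented/Cementless patella usage".

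**The concern.** A radiographic interface reading asks how the component sits against bone, and the two patellae meet bone differently. Table 10-2 describes the cemented patella as polyethylene for cemented use only. For the other it says: "The cementless patellar components are manufactured from UHMWPE overmolded onto 3D printed titanium conforming to" an ASTM standard, with a 3D-printed porous surface facing the bone. A combined rate averages two fixation mechanisms and describes neither.

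The plan treats patella fixation as relevant to operating time but does not use it where fixation itself is assessed. If a radiographic problem were confined to cementless patellae, the combined table would understate it, and more so the smaller their share of the resurfaced knees. A split made later from the stored data would be possible, but it would not be prespecified. Section 3.1 says the study data will support CE mark registration of the tibial base, so a breakdown chosen after seeing results would be open to a charge of selection.

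**Working it through.** **The plan's own figures.** The documents give no sample size, rate or precision target for patellar radiographs. The only sample-size calculation is in section 9.7: 191 knees, raised to 225 for 15% attrition. It reproduces: n = [(1.645·√(0.85·0.15) + 0.842·√(0.91·0.09)) / 0.06]² = 190.5, rounded up to 191; and 191 / 0.85 = 224.7, rounded up to 225. It concerns the KOOS responder rate and has no bearing here.

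**Step 1: which strata reach the endpoint.**

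| Analysis | Primary/revision | CR FB/PS FB | Cemented/cementless patella |
|---|---|---|---|
| Patellar radiographs (9.8.4, 9.8.4.2) | yes | yes | not specified |
| Duration of surgery (9.8.4.3) | not stated in 9.8.4.3 | not stated in 9.8.4.3 | yes |

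Both knee configurations and both procedure types may receive either patella, so none of the listed strata separates the two.

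**Step 2: how far a combined rate could move.** With n_c cementless and n_m cemented knees imaged, and finding rates p_c and p_m:

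combined rate = (n_c·p_c + n_m·p_m) / (n_c + n_m)

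All inputs are assumptions. The first rate column takes p_c = 5%, the second p_c = 10%; p_m = 1% throughout. The rows total 600 knees, the study minimum, except the second, which leaves 200 unresurfaced.

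| Cementless | Cemented | Combined, 5% vs 1% | Combined, 10% vs 1% |
|---|---|---|---|
| 300 | 300 | (15 + 3)/600 = 3.0% | 5.5% |
| 300 | 100 | (15 + 1)/400 = 4.0% | 7.75% |
| 150 | 450 | (7.5 + 4.5)/600 = 2.0% | 3.25% |
| 50 | 550 | (2.5 + 5.5)/600 = 1.3% | 1.75% |

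If the two true rates were equal, there would be no dilution.

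**Step 3: what a separate cementless result could show.** For zero findings in n knees the exact two-sided 95% upper bound is 1 − 0.025^(1/n). Non-zero counts use the Clopper-Pearson interval.

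| Cementless knees imaged | Findings | Exact 95% CI |
|---|---|---|
| 300 | 0 | 0 to 1.2% |
| 300 | 6 (2%) | 0.7 to 4.3% |
| 300 | 15 (5%) | 2.8 to 8.1% |
| 255 (300 less 15%) | 0 | 0 to 1.4% |
| 100 | 0 | 0 to 3.6% |
| 50 | 0 | 0 to 7.1% |

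Precision therefore depends on uptake and on how many knees are imaged. Section 8.2.4.1 makes radiographs optional at alternative visits (mailed questionnaires plus a phone contact), so the imaged number can fall below the implanted number.

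**Step 4: what a comparison could show.** Take 12/300 cementless (4.0%, 95% CI 2.1 to 6.9%) and 2/200 cemented (1.0%, 0.1 to 3.6%), again assumed. The combined 14/500 = 2.8% lies inside both intervals, and Fisher's exact test gives p = 0.054. Even a fourfold difference at nearly full uptake need not separate the groups clearly. The split is worth having for description, not as a test.

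**The case against.** The best defence is scope. Section 2 makes the tibial base the focus, the short title names only the tibial base, survivorship is defined for it alone, and section 3.1 ties the CE mark purpose to it. The revision history in Exhibit E records that the focus on the cementless patella was withdrawn. A reader who starts from the full title, which still names the cementless patella, might infer that a main study device has been left without a result. The current text does not support that: a narrower role for the patella looks deliberate. But the patellar radiographic endpoint was retained, and a retained endpoint should be readable.

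Second, the plan nowhere says the two types will be pooled. Mixing follows from the listed strata. Nor is information lost: Table 8-1 has the Device Log record product codes, and Exhibit C gives cemented and cementless patellae different codes. What is missing is prespecification, not data.

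Third, a reader might take the cap to mean that 300 cementless patellae will be implanted and imaged. It is conditional, has no minimum, and imaging is optional at some visits.

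Fourth, one might extend the point to adverse events, patellar revisions, an unresurfaced group or the duration analysis. No comparable defect is shown there. A patellar revision requires its own adverse event and revision forms under section 8.6, and duration is already stratified.

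Finally, the groups would be confounded by surgeon and calendar time, because fixation is the surgeon's choice and depends on product availability. That stands, and it limits how the split may be read.

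**Conclusion.** The point holds for one table. As written, patellar radiographic findings would be summarised across two components with different bone interfaces, and none of the prespecified breakdowns separates them. Splitting by fixation type is a better method than the stated strata.

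The size is unknown. The 1.3% to 4.0% range rests on assumed rates of 5% and 1% and assumed mixes, and shows only that dilution could be material. Whether a separate cementless result is informative depends on uptake, with a zero-event upper bound between 1.2% (300 knees imaged) and 7.1% (50 knees). The documents do not support the inference that a fixation problem is expected or would certainly be hidden. The primary endpoint, its sample size and the study success decision are not affected.

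**What to change.** In section 9.8.4.2, state that patellar radiographic findings will be tabulated separately for cemented and cementless patellae at each time point. The denominator should be knees that have that component and a radiograph in the window, reported with exact 95% confidence intervals. Label the table descriptive, because fixation is chosen by the surgeon and depends on product availability, so differences between the groups are not causal comparisons.

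The cost is a few lines of text and one table layout. The product codes in the Device Log already identify the component, so no new form, visit, radiograph or subject is needed. The wording should be settled before the radiographic data are reviewed.

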8.5 Post-operative Withdrawal of Enrolled Subjects

A post-operative withdrawal is a Subject who has signed the Informed Consent Document (ICD), has been implanted with a study device, and is later withdrawn from study participation (i.e., withdrawal of consent, revision of any study TKA component, death, etc.). Table 8-9 describes post-operative withdrawal scenarios and the eCRF to be completed. Further description of revision is provided in Section 8.6 Revisions. No data after the date of withdrawal will be included in the clinical analysis.

Table 8-9: Post-operative Withdrawal Scenarios

Example	Action	Follow Up
Subject withdraws consent	 Study site documents Subjects' request for withdrawal from study. Complete Study Completion/Discontinuation eCRF 	Do not continue
Surgeon preference / medical opinion	 Study site documents Surgeons' reason for patient withdrawal from study (should occur under very limited conditions, in order to avoid investigator bias). Complete Study Completion/Discontinuation eCRF 	Do not continue
Death	Complete Adverse Event eCRF Complete Study Completion/Discontinuation eCRF	Do not continue
Revision	See Section 8.6 and Table 8-10 Revision Examples	

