8.6 Revisions

A "revision" is defined as a surgical procedure of the affected knee where one or more of the TKA components (metal femoral component and/or metal tibial base, polyethylene insert, or patella polyethylene resurfacing component) are removed. Should it be necessary for the Subject to undergo a revision of any ATTUNE Cementless Femoral and/or Tibial Base component between the time of enrolment and completion of the study data acquisition, the Subject is to be withdrawn from study participation. Thus, both an Adverse Event (AE) eCRF and the Subject Completion/Discontinuation eCRF must be completed (see Table 8-9). Note that if a tibial insert is exchanged and/or a resurfaced patella is revised, but both the femoral and tibial base components remain, then an AE eCRF must be completed, but the subject is not to be withdrawn from the study.

A "re-operation" is defined as any surgical procedure of the affected knee in which none of the TKA components are removed. Examples include irrigation & debridement without tibial insert exchange or the resurfacing of a previously unresurfaced patella. These subjects are not to be withdrawn. An Adverse Event (AE) eCRF must be completed.

Table 8-10: Revision and Reoperation Examples

Example	Actions	Follow Up
Removal / revision of metal Tibial Base and/or Femoral component	 Complete Adverse Event eCRF Complete Revision/Reoperation eCRF Complete Study Completion/Discontinuation eCRF 	Do not continue
Tibial Insert polyethylene exchange	Complete Adverse Event eCRF Complete Revision/Reoperation eCRF	Continue
Revision of a previously resurfaced patella	 Complete Adverse Event eCRF Complete Revision/Reoperation eCRF 	Continue
Resurfacing of a previously unresurfaced patella in combination with a Tibial polyethylene exchange	 Complete Adverse Event eCRF Complete Revision/Reoperation eCRF 	Continue

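### The Kaplan-Meier endpoint carries the tibial base's name, but its only event definition is removal of any knee component, so one label covers two different estimates

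*Combined protocol and SAP*

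**What the plan says.** Section 9.8.4.2 lists as a secondary endpoint "Implant survivorship of the ATTUNE Cementless FB Tibial Base using Kaplan-Meier survival analysis at 1, 2 and 5 year timepoints". Sections 6.2 and 6.3 and Section 9.8.4.3 use the same device name, with years 3 and 4 as tertiary or additional time points.

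The event is specified in one place only, later in Section 9.8.4.2: "A Kaplan-Meier survivorship model will be used to estimate survivorship rates (where a revision is defined in Section 8.6". Section 8.6 defines a revision as an operation on the study joint "where one or more of the TKA components (metal femoral component and/or metal tibial base, polyethylene insert, or patella polyethylene resurfacing component) are removed". Section 9.6 calls the analysis a Kaplan-Meier analysis of revisions and assigns it to the Safety set. Neither section limits the event to the base.

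Section 8.6 and Table 8-10 foresee procedures that leave the base in place. After an insert exchange or patella revision with both metal components retained, an adverse event form is completed, "but the subject is not to be withdrawn from the study". Withdrawal applies when it is necessary to "undergo a revision of any ATTUNE Cementless Femoral and/or Tibial Base component".

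Section 8.5, however, lists among its withdrawal examples "revision of any study TKA component, death, etc". The same section then defers: "Further description of revision is provided in Section 8.6 Revisions", and its table says "See Section 8.6 and Table 8-10 Revision Examples".

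**The concern.** The endpoint's name and its event rule describe different quantities. The name asks how long the tibial base stays in place; the rule, read literally, asks how long the knee goes without any component being removed. The plan does not say whether a base-sparing revision is an event, a censoring time or neither.

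The base is the device whose CE mark registration these data are meant to support (Section 3.1). A survivorship figure under its name, at 1 to 5 years, could include removals of other components, some of which are separately approved: the femoral components already hold a CE mark (Exhibit C, Table 13-1). Section 9.8.4 also requires each endpoint separately for the CR FB and PS FB configurations. The same events fall there on about half as many knees, so each one moves the estimate about twice as far.

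If the text stays as it is, the choice between the two readings could be made after the revisions are known.

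**Working it through.** The plan states no expected survivorship, revision rate or event count, so it has no figure of its own to reproduce. The check covers direction, then size per event, then an illustration with assumed counts.

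**Direction.** Let T_any be the time to first removal of any component and T_base the time to removal of the base. Removal of the base is itself removal of a component, so T_any ≤ T_base in every knee, and S_any(t) ≤ S_base(t). The two are equal only if no base-sparing revision occurs by time t.

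This orders the quantities being estimated, not every sample. Counter-example with 10 knees: one has an insert exchange at time 1 and base removal at time 3, five are censored at time 2, and four are followed to time 5. At time 4 the any-component estimate is 1 − 1/10 = 0.90 and the base-only estimate is 1 − 1/5 = 0.80. Such reversals were rare in simulation (600 knees, 5 years, assumed 25% cumulative loss, nine scenarios of assumed rates, 400 runs each): the any-component estimate was the higher one in at most 0.25% of runs.

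**Size per event.** One added event lowers the estimate by about 1/n at risk. Inputs: 600 knees in all and 300 per configuration (Section 9.1).

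- All knees: 1/600 = 0.17 percentage points.
- One configuration: 1/300 = 0.33 points.
- If 15% are no longer at risk: 1/510 = 0.20 and 1/255 = 0.39 points. The 15% is borrowed from Section 9.7, where it is the 1-year attrition allowance for the primary endpoint. It is used here only to show sensitivity.

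**Illustration (counts assumed).** No censoring, S = 1 − d/n, Greenwood variance, and the two-sided log-log 95% interval that Section 9.8.4.2 specifies.

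| Knees | Events counted | Estimate | 95% CI |
|---|---|---|---|
| 600 | 6 base removals | 99.0% | 97.79 to 99.55 |
| 600 | 6 + 3 base-sparing | 98.5% | 97.14 to 99.22 |
| 600 | 6 + 6 base-sparing | 98.0% | 96.51 to 98.86 |
| 600 | 6 + 12 base-sparing | 97.0% | 95.28 to 98.10 |
| 300 | 3 base removals | 99.0% | 96.93 to 99.68 |
| 300 | 3 + 3 base-sparing | 98.0% | 95.60 to 99.10 |

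With 3 or 6 added events in 600 knees, the any-component estimate stays inside the base-only interval. It takes 8 (14/600 events, 97.67%) to fall below the lower limit of 97.79%, and 7 in 300 knees (10/300 events, 96.67%, against 96.93%). This only gives scale; it is not a test, because both curves use the same knees.

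**Range under assumed 5-year rates.** Take base removal at 1 to 3%, insert or patella revision at 0.5 to 3% and femoral-only removal at 0.25 to 1%, acting independently. Then S_any = (1 − base)(1 − insert/patella)(1 − femoral).

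- Smallest gap: 0.97 × 0.995 × 0.9975 = 96.27%, against 97.0% for the base, a gap of 0.73 points.
- Largest gap: 0.99 × 0.97 × 0.99 = 95.07%, against 99.0%, a gap of 3.93 points.

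**Femoral-only removal in a base-only curve.** Section 8.6 withdraws these subjects, so later base removal is not observed. Worst ordering, with 6 femoral-only removals before 6 base removals:

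- 600 knees: censoring gives 1 − S = 6/594 = 1.010%; treating them as a competing event gives 6/600 = 1.000%.
- 300 knees: 6/294 = 2.041%, against 6/300 = 2.000%.

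The differences are 0.010 and 0.041 points, so at these counts simple censoring is adequate.

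**The case against.** The strongest reply is that the plan already means the base. The endpoint is named for it, and Section 8.6 itself speaks of revision component by component. The parenthesis in Section 9.8.4.2 may only separate revision from re-operation. That reading is plausible, so it cannot be said that base-sparing revisions will certainly be counted against the base. But no sentence adopts it, and the literal reading is at least as close to the text. Two tenable readings that give different numbers are the defect.

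A second reply is that any-component revision is a coherent and conservative event, and that an insert exchange can bear on the base: Exhibit B defines component disassociation as the insert dislodging from it. This stands as a reason to keep the any-component curve, under its own name.

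Third, the size is not anchored and the consequence is limited. This stands. The figures above rest on assumed counts or rates, and Section 9.4 states that the primary hypothesis is the only one in the study.

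A reader might also infer that the reported figure can only be too low. The documents do not support that. The direction holds in expectation and for the event definition alone. Equality is possible, single samples can reverse, and other features, such as loss to follow-up or loose bases never revised, could push the estimate upward.

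**Conclusion.** The point holds as a mismatch between the endpoint's label and its event rule. On the literal reading, the survivorship reported for the base is expected to be no higher than true base survivorship, with a shortfall of roughly 0.17 points per base-sparing first revision in 600 knees and 0.33 in 300. The total cannot be derived from the documents; about 0.7 to 3.9 points at 5 years follows only under the assumed rates shown. The bias would run against the device. It would be wrong to infer that the trial's conclusion is at risk, since survivorship has no hypothesis or threshold and study success does not depend on it.

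Two smaller points belong with this one.

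- **Analysis set.** Section 9.6 gives the Kaplan-Meier analysis to the Safety set without a time limit, but by default gives tertiary endpoints, which include years 3 and 4, to the Per Protocol set. The specific rule probably governs, but the plan should say so.
- **Withdrawal wording.** The example in Section 8.5 is out of line with Sections 8.4 and 8.6 and Table 8-10. Because Section 8.5 excludes data after withdrawal, the wording decides whether a base removal that follows an insert or patella revision is seen. That matters for a base-only curve and not for time to first any-component revision.

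**What to change.** In Sections 9.8.4.2 and 9.8.4.3:

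1. Define the event for the tibial base curve as first removal of the tibial base for any reason.
2. Report any-component revision, as Section 8.6 defines it, as a second Kaplan-Meier curve under its own label.
3. In the base curve, censor femoral-only removal at the date of withdrawal, and keep knees with an insert or patella revision at risk for as long as they remain in follow-up.

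Also state in Section 9.6 that the Safety set applies to every Kaplan-Meier time point, including years 3 and 4. Reconcile the withdrawal example in Section 8.5 with Section 8.4, Section 8.6 and Table 8-10; which follow-up rule applies is for the sponsor to settle.

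The cost is wording and one extra Kaplan-Meier run. Exhibit B already asks for the components removed at each revision, so no new data are needed.
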